5.7. Other Analyses

5.7.1. Pharmacokinetics

All HHCs who received at least 1 dose of study drug and have at least 1 plasma concentration value after administration will be included in the analysis. Individual JNJ-64281802 plasma concentrations will be listed and summarized with descriptive statistics (n, mean, SD, geometric mean, median, minimum, maximum and interquartile ranges) by dose. Individual and summarized plasma concentration results may be graphically presented by dose and at selected time points. In this graphical presentation, special attention will be given to plasma concentration profiles of HHCs who have a lab-confirmed DENV infection between baseline and the last day of dosing + 1 day. Special attention to plasma concentration-time profiles may also be given to individuals with SAEs.

5.7.2. Viral Genome Sequencing

DENV viral genome sequence analysis will be performed to evaluate the presence of polymorphisms and genetic variations on the amino acid level and to define the serotype/genotype of the DENV virus.

Sequencing is focused on a predefined list of positions of interest.

The list of positions of interest might be updated during the analysis.

Polymorphisms, ie, genetic variations, are defined as amino acid changes from serotype-specific DENV reference sequences.

Wild type: If at certain position the amino acid in the participant sequence matches the reference sequence, that is no genetic variation is present at that position, the virus is considered to be wild type at that position.

Number (%) of participants with a specific substitution and number (%) of participants with a specific DENV serotype/genotype will be analysed.

Frequencies and percentages will be presented for the specified parameters. The denominator is the number of participants with sequencing data. Summaries will be provided by subgroups and intervention groups.

A separate SAP and virology report may be prepared.

5.7.3. Biomarkers

Statistical approaches to explore correlations between clinical outcome and blood biomarkers vary and depend on the different data types of the applied technology platforms, as well as on the extent of observed differences between participants. Analyses will be conducted at the sponsor's

discretion and are not part of this SAP. The analyses will always be under the supervision of the sponsor.

Results will be presented in the main study report or a separate report.

5.7.4. Data Monitoring Committee (DMC) or Other Review Board

An IDMC was commissioned for this study and reviewed unblinded safety data on a regular basis throughout the conduct of this study to ensure participant safety. The committee did meet periodically to review these safety data.

At any point during the study, following any reviews of safety, PK and/or IAs data, the IDMC had the authority to recommend to the Sponsor Committee modifications to the study conduct and/or to the safety assessments, or to halt a dose arm due to safety concerns. Based on the recommendations of the IDMC, the Sponsor Committee could decide that changes to the study should be implemented.

Further details on the composition of the IDMC, the content of the data package and the frequency of the meetings are available in the IDMC charter.

The regular IDMC analyses followed this SAP, but data was restricted to the following:

Index Case Data		
Index cases	section 6.3	
General Information Data		
Participant Dispositions	section 5.2	
Demographics and Baseline Characteristics	section 6.4	
Protocol Deviations	section 6.5	
Extent of Exposure	section 5.6.1	
Efficacy Data		
Primary Endpoint(s) Analysis	section 5.3	
Safety Data		
Adverse Events	section 5.6.2	
Clinical Laboratory Tests	section 5.6.3.1	
Vital Signs and Physical Examination	section 5.6.3.2	
Electrocardiogram	section 5.6.3.3	
Other Analyses Data		
Pharmacokinetics	section 5.7.1	

A Separate DPS specifying the outputs created for the IDMC analyses is also produced.

6. SUPPORTING DOCUMENTATION

6.1. Appendix 1 List of Abbreviations

AE adverse event

ATC anatomic and therapeutic class

AUC area under the curve

 AUC_{τ} area under the concentration curve during one dosing interval

BMI body mass index
CI confidence interval
Cmax maximum concentration

CPAP Clinical pharmacology analysis plan

CRF Case report form

C_{trough} observed analyte concentration just prior to the beginning or at the end of a dosing interval

DENV Dengue virus

DMC Data Monitoring Committee
DPS Data Presentation Specifications

ECG electrocardiogram FA Final analysis

FDA Food and Drug Administration

HDR High dose regimen
HHC Household contact
IA Interim Analysis
ICF Informed consent form

IDMC Independent data monitoring committee

Ig Immunoglobulin

IWRS interactive web response system

LD Loading dose
LDR Low dose regimen
LLOD lower limit of detection
LLOQ Lower limit of quantification

MD Maintenance dose

MedDRA Medical Dictionary for Regulatory Activities

MSR Modelling and simulation report

NAb neutralizing antibodies
NS Non-structural protein
PCR Polymerase chain reaction
PD pharmacodynamic(s)
PE Prophylactic efficacy
PK pharmacokinetic(s)
PoC Proof-of-concept

qPCR Quantitative polymerase chain reaction

RNA Ribonucleic acid
RT Reverse transcription
SAE serious adverse event
SAP Statistical analysis plan
SAS Statistical analysis sofware

SD standard deviation SE Standard error

SMQs standardised MedDRA queries SSG Statistical support group Tmax time to maximum concentration

VL Viral Load

WHO World Health Organization

WHO-DD World Health Organization Drug Dictionary

6.2. Appendix 2 Changes to Protocol-Planned Analyses

- 1) Minor updates and clarifications are made to the primary estimand when compared to the definition in the protocol. The modifications are done based on the available data and new insights on the detectability of a laboratory confirmed DENV infection using different assays:
 - 1 extra day is added to the observation period of the endpoint because for some participants the Day 28 assessment is performed 1 day after the last dose,
 - intercurrent events are modified and clarified: fasted intake of study intervention is not considered as intercurrent event based on the quality of the data collected for this purpose, clarifications are added to the missed doses and treatment interruptions, overdose of study intervention and wrong IP have been added as intercurrent events.
 - the stratification factor 'country' is updated to 'region' in the logistic model used for the primary estimand of the prophylactic efficacy to avoid quasi-complete separation of data points due to the low number of events. Similarly, region is used as the stratification factor in the Mantel-Haenszel stratum-weighted estimator of the risk difference.
 - the 2-sided confidence interval was updated to a corresponding 1-sided confidence interval.
- 2) The definition of the complete study population is updated to "All participants included in the primary or secondary study population": a minimum of DENV RNA and/or NS1 protein assay data should be available to be able to confirm by laboratory data that the signs and symptoms are caused by a DENV infection.
- 3) The study was prematurely ended on 02 October 2024 when 21 laboratory confirmed dengue infections between baseline and last day of dosing (+1 day) were observed in the primary analysis population and 14 symptomatic dengue infection between baseline and last day of dosing (+1 day) were observed in the complete study population. This decision was taken by Johnson & Johnson based on portfolio reprioritization and was not based on any safety concerns.

Because of this early termination, the following changes to the per protocol-planned analyses are done: the planned IA is skipped, the sensitivity estimators for the primary objective are not calculated, the PK analyses is restricted to descriptive statistics on the individual plasma concentration-time data, the PK/PD analyses are not done, some exploratory analyses are left out and the analysis is considered final.

The following exploratory analysis are left out:

- Exploratory analysis on the prophylactic effect of JNJ-64281802 with respect to the prevention of DENV infection as measured by DENV ribonucleic acid (RNA)
- Exploratory analysis on the prophylactic effect of JNJ-64281802 as measured through detection of DENV NS1 protein

It is clear from the available data that all laboratory confirmed DENV infections have detectable RNA on at least 1 time point, while only a minority have detectable DENV NS1 protein.

- Exploratory analysis to evaluate the prophylactic effect of JNJ-64281802 with respect to the prevention of symptomatic DENV infection up to Day 40, Day 50 and Day 90

Only isolated cases of symptomatic DENV infections after the last dose of study intervention are observed.

6.3. Appendix 3 Index Cases

Index cases will participate for one visit only.

Disposition

The number of Index cases in the following disposition categories will be summarized:

- Index cases enrolled
- Index cases for which the DENV infection was confirmed by the central lab test

An overview will be provided by region, country and site ID, showing per index case the number of HHCs (1, 2, 3 or > 3) that entered in the trial.

A summary will be provided of the different serotypes per region/country and clinical site.

Viral sequencing.

Exploratory analysis will be done to determine the circulating DENV serotypes/genotypes among the index cases.

6.4. Appendix 4 Demographics and Baseline Characteristics of the HHCs

The number of participants in each analysis set will be summarized and listed by intervention group and overall. In addition, the distribution of participants by region, country, and site ID will be presented unless otherwise noted.

Table 8 presents a list of the demographic variables that will be summarized by intervention group and overall for the primary, secondary and safety analysis set.

Table 8: Demographic Variables

Continuous Variables:	Summary Type
Age ([years])	Descriptive statistics (N, mean,
Weight (kg)	standard deviation [SD], median
Height (cm)	and range [minimum and
Body Mass Index (BMI) (kg/m ²)	maximum]).
Categorical Variables	
Age ([≤25 years, 26-40 years, 41-55 years, and > 55 years])	
Sex (male, female, undifferentiated)	
Race ^a (American Indian or Alaska Native, Asian, Black or African	
American, Native Hawaiian or other Pacific Islander, White, Multiple)	Frequency distribution with the number and percentage of participants in each category.
Ethnicity (Hispanic or Latino, not Hispanic or Latino)	
BMI ([underweight <18.5 kg/m2, normal 18.5-<25 kg/m2, overweight 25-	
<30 kg/m2, obese >=30 kg/m2)	
Region ((Asia-Oceania (APAC), Europe and Middle East and Africa	
(EMEA), North America (NA), and Latin America and the	
Caribbean (LATAM))	
Country	
Baseline Serology (IgG) (<16 relative units (RU)/mL (negative); ≥16 to <22	
RU/mL (borderline); ≥22 RU/mL (positive))	

^aIf multiple race categories are indicated, the Race is recorded as 'Multiple'

6.5. Appendix 5 Protocol Deviations

In general, the following list of major protocol deviations may have the potential to impact participants' rights, safety or well-being, or the integrity and/or result of the clinical study. Participants with major protocol deviations will be identified prior to database lock and the participants with major protocol deviations will be summarized by category.

- Developed withdrawal criteria but not withdrawn
- Entered but did not satisfy criteria
- Received a disallowed concomitant treatment
- Received wrong treatment or incorrect dose
- Missed doses
- Other

6.6. Appendix 6 Prior and Concomitant Medications

Prior and Concomitant medications will be coded using the World Health Organization Drug Dictionary (WHO-DD). Prior medications are defined as any therapy used before the day of first dose (partial or complete) of study intervention. Concomitant medications are defined as any therapy used on or after the same day as the first dose of study intervention, including those that started before and continued after the first dose of study intervention.

Summaries of concomitant medications will be presented by ATC1 and ATC2 term, standardized medication name, intervention group, and study phase (prophylactic, follow-up and combination of prophylactic and follow-up). The proportion of participants who receive each concomitant medication will be summarized as well as the proportion of participants who receive at least 1 concomitant medication.

Prior medications will be listed.

6.7. Appendix 7 Medical History

The medical history will be listed.

6.8. Appendix 8 Laboratory Related Adverse Events Coded Terms

The following adverse events are related to laboratory assessments and will be assigned to the screening phase when the start date equals the date of first study drug intake:

AEBODSYS	AEDECOD
Blood and lymphatic system disorders	Anaemia
Blood and lymphatic system disorders	Eosinophilia
Blood and lymphatic system disorders	Hypochromic anaemia
Blood and lymphatic system disorders	Iron deficiency anaemia
Blood and lymphatic system disorders	Leukocytosis
Blood and lymphatic system disorders	Lymphadenopathy
Blood and lymphatic system disorders	Microcytic anaemia
Blood and lymphatic system disorders	Neutropenia
Blood and lymphatic system disorders	Normochromic normocytic anaemia
Blood and lymphatic system disorders	Normocytic anaemia
Blood and lymphatic system disorders	Thrombocytopenia
Blood and lymphatic system disorders	Thrombocytosis
Hepatobiliary disorders	Hyperbilirubinaemia
Infections and infestations	Asymptomatic bacteriuria
Infections and infestations	Pyuria
Investigations	Activated partial thromboplastin time prolonged
Investigations	Alanine aminotransferase decreased
Investigations	Alanine aminotransferase increased
Investigations	Amylase increased
Investigations	Aspartate aminotransferase decreased
Investigations	Aspartate aminotransferase increased
Investigations	Bacterial test
Investigations	Blood alkaline phosphatase
Investigations	Blood alkaline phosphatase increased
Investigations	Blood bilirubin increased
Investigations	Blood cholesterol increased
Investigations	Blood creatine phosphokinase
Investigations	Blood creatine phosphokinase increased
Investigations	Blood glucose decreased
Investigations	Blood glucose increased
Investigations	Blood lactate dehydrogenase increased
Investigations	Blood phosphorus decreased
Investigations	Blood potassium increased
Investigations	Blood pressure increased
Investigations	Blood triglycerides increased
Investigations	Blood uric acid increased
Investigations	Blood urine present

	•
Investigations	Gamma-glutamyltransferase increased
Investigations	Glucose urine present
Investigations	HIV test positive
Investigations	Haemoglobin decreased
Investigations	Hepatic enzyme increased
Investigations	Lipase increased
Investigations	Low density lipoprotein increased
Investigations	Lymphocyte count decreased
Investigations	Nitrite urine present
Investigations	Platelet count decreased
Investigations	Protein urine
Investigations	Protein urine present
Investigations	Prothrombin time prolonged
Investigations	Red blood cell sedimentation rate
Investigations	Red blood cell sedimentation rate increased
Investigations	Red blood cells urine
Investigations	Red blood cells urine positive
Investigations	Transaminases increased
Investigations	Urine ketone body present
Investigations	White blood cell count
Investigations	White blood cell count increased
Investigations	White blood cells urine
Investigations	White blood cells urine positive
Metabolism and nutrition disorders	Diabetes mellitus
Metabolism and nutrition disorders	Dyslipidaemia
Metabolism and nutrition disorders	Hyperamylasaemia
Metabolism and nutrition disorders	Hypercalcaemia
Metabolism and nutrition disorders	Hypercholesterolaemia
Metabolism and nutrition disorders	Hyperglycaemia
Metabolism and nutrition disorders	Hyperkalaemia
Metabolism and nutrition disorders	Hyperphagia
Metabolism and nutrition disorders	Hypertriglyceridaemia
Metabolism and nutrition disorders	Hyperuricaemia
Metabolism and nutrition disorders	Hypoalbuminaemia
Metabolism and nutrition disorders	Hypocalcaemia
Metabolism and nutrition disorders	Hypoglycaemia
Metabolism and nutrition disorders	Hypokalaemia
Metabolism and nutrition disorders	Hyponatraemia
Metabolism and nutrition disorders	Hypophosphataemia
Metabolism and nutrition disorders	Hypoproteinaemia
Metabolism and nutrition disorders	Impaired fasting glucose
Metabolism and nutrition disorders	Type 2 diabetes mellitus

NCT05201794

Statistical Analysis Plan 64281802DNG2004

Renal and urinary disorders	Glycosuria
Renal and urinary disorders	Haematuria
Renal and urinary disorders	Leukocyturia
Renal and urinary disorders	Proteinuria

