5.1.1. Analysis Phase Definition

The Prophylactic Dosing phase used for the safety evaluation and as defined below is extended compared to the Prophylactic Dosing phase as defined in the protocol considering the long half-life (~10 days) of the study intervention.

Following analysis phases are defined:

Table 1: Construction of analysis phases

Analysis phase Start date		End date		
Screening	The date &	& time of signing the 1 minute before date & time of first study drug intake**.		
(phase 1)	informed cor	nsent*		
Prophylactic	DosingDate & time	of first study drug intake**	Minimum of:	
(phase 2)	(JNJ - 64281	802 or Placebo)	a. Date of Day 50 Visit at 23.59h***	
			b. Date of study termination at 23.59h	
Follow-up	End of the P	rophylactic Dosing phase	Study termination date (date of last contact) at 23.59h	
(phase 3) ***	+1 minute			

^{*:} if no time is available then impute with 00:00

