5.6.2. Adverse Events

The verbatim terms used in the CRF by investigators to report adverse events will be coded using the Medical Dictionary for Regulatory Activities (MedDRA version 25.0). Any AE occurring at or after the initial administration of study intervention until the last study-related activity, or until

the participant has been deemed lost to follow-up after demonstration of due diligence of follow-up efforts will be considered as treatment emergent. If the event occurs on the day of the initial administration of study intervention, and either event time or time of administration are missing, then the event will be assumed to be treatment emergent (TE), unless the AE is reported based on a baseline laboratory result, in which case the AE will be assigned to the screening phase. The list of coded AE terms that are based on a laboratory result is included in appendix 8 (section 6.8). If the event date is recorded as partial or completely missing, then the event will be considered as treatment emergent unless it is known to be prior to the first administration of study intervention based on partial onset date or resolution date. All reported adverse events will be included in the analysis. For each adverse event, the number and percentage of participants who experience at least 1 occurrence of the given event will be summarized by intervention group.

Separate tables and participants listings will be created for solicited (see Table 3) and unsolicited adverse events, showing the results by study intervention group.

Summary tables by study intervention group will be provided for adverse events by phase (Prophylactic Dosing, Follow-up and both phases combined):

- AEs
- Serious AEs (SAEs)
- AEs leading to discontinuation of study intervention/termination of study participation
- AEs by toxicity grade assigned by the investigator, based upon protocol appendix 9.
- AEs by relationship to study intervention
- AEs leading to dose interruption of study intervention

In addition to the summary tables, participants listings will be provided for participants who:

- Had SAEs
- Had AEs leading to discontinuation/interruption of study intervention or termination of study participation

A listing of participants who died will be provided.

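### SAP Appendix 8 moves listed Day 1 adverse events to screening by date alone and lists three non-laboratory terms, so a post-dose event with one of those terms can drop out of the treatment-emergent tables

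*SAP*

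**What the plan says.** Four places bear on where a Day 1 adverse event is counted.

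- **SAP 6.8 (Appendix 8)** gives a list of coded terms and states that they "will be assigned to the screening phase when the start date equals the date of first study drug intake".
- **SAP 5.6.2** makes events at or after first administration treatment-emergent. For an event on the day of first dosing "and either event time or time of administration are missing, then the event will be assumed to be treatment emergent (TE"). The exception attached to that default reads "unless the AE is reported based on a baseline laboratory result, in which case the AE will be assigned to the screening phase". The section then points to the list that puts the exception into practice: "The list of coded AE terms that are based on a laboratory result is included in appendix 8 (section 6.8").
- **SAP 5.1.1, Table 1** ends the screening phase "1 minute before date & time of first study drug intake", so phase is set by date and time.
- **Protocol 9.4.4.1** treats any adverse event at or after the first administration as treatment-emergent and has no exception by coded term.

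The SAP's adverse event tables are restricted by phase: "Summary tables by study intervention group will be provided for adverse events by phase (Prophylactic Dosing, Follow-up and both phases combined"). Screening is not among the phases tabulated. SAP Appendix 2 (section 6.2), which records changes from the protocol analysis, does not mention the Day 1 reassignment.

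The Appendix 8 list includes "Lymphadenopathy", "Blood pressure increased" and hyperphagia.

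**The concern.** The body of the SAP and its appendix give different answers for the same event. In 5.6.2 the move to screening is an exception to a missing-time default and requires that the event came from a baseline laboratory result. In Appendix 8 the move needs only a listed term and a matching date. A programmer cannot follow both when a listed event has a recorded Day 1 onset after dosing.

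The list makes this more than a drafting slip. Lymph nodes are part of the physical examination (protocol 8.2.1), blood pressure is a vital sign (protocol 8.2.2), and hyperphagia is a symptom. The justification for the rule, that the event reflects a baseline laboratory sample, does not apply to any of them.

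At stake is the accuracy of the treatment-emergent counts on a day with real post-dose time at risk. Two loading doses are taken on Day 1, in the main study the first at the site and the second at home (protocol 1.3.2.2, footnote c, and 6.1). An event that truly follows dosing could be classed as pre-treatment and disappear from the summaries.

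**Working it through.** There is no plan figure to reproduce. The check is a comparison of the rules, plus a count of the list.

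**Count of Appendix 8 terms by system organ class.** Blood and lymphatic 12, hepatobiliary 1, infections 2, investigations 45, metabolism 19, renal 4. Total: 12 + 1 + 2 + 45 + 19 + 4 = 83. Clearly not laboratory results: 3. Share: 3/83 = 3.6%. Some other terms, such as hypoglycaemia, haematuria and diabetes mellitus, could be either laboratory or clinical and are not counted here.

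**The rules applied to Day 1 cases.**

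| Day 1 event | SAP 5.6.2 as worded | SAP Table 1 and protocol 9.4.4.1 | Appendix 8 |
|---|---|---|---|
| Laboratory term from the predose sample, time missing | Screening | Before first dose by sample time | Screening |
| Laboratory term from the predose sample, recorded time after dosing because the result came back later | Emergent, since no time is missing | Before first dose by sample time, emergent by recorded time | Screening |
| Blood pressure or lymph node finding at the screening visit on the same date, recorded before dosing | Not emergent | Screening | Screening |
| Any of the three non-laboratory terms, recorded onset after the first dose | Emergent | Emergent | Screening |
| Any of the three non-laboratory terms, time missing | Emergent by its stated principle, screening if applied through the list | Not determinable without a time | Screening |

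Reading the rows:

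1. For laboratory terms the date rule usually gives the right answer. The Day 1 haematology, chemistry, coagulation and urinalysis samples are marked predose in protocol 1.3.2.2, and the next scheduled ones are on Day 13. Only an unscheduled post-dose draw on Day 1 would be misplaced. In the second row Appendix 8 does better than 5.6.2 read literally, because baseline results are not available at randomization (protocol 7.1).
2. In the fourth row Appendix 8 contradicts the other three sources, with no laboratory rationale for doing so.
3. In the fifth row, letting 5.6.2 govern does not cure the problem. That section identifies laboratory-based events through this list, so a non-laboratory term on it inherits the exception.
4. Every reassignment runs from the dosing phase to screening and none runs the other way, so emergent counts can only fall.

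The number of events affected cannot be computed, because neither document gives Day 1 adverse event counts.

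**The case against.** The best defence is that Appendix 8 is not a separate rule. It is the lookup list for the exception in 5.6.2, with an abbreviated header, and should be read with its parent section. For nearly all its terms the date rule then does what is intended: it keeps baseline abnormalities out of the emergent counts even when they are reported after dosing.

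Two of the three questioned terms may also often be predose. Vital signs and the physical examination are done at screening, and dosing should start within 12 hours of consent (protocol 1.3.2.1), so both can share a calendar date with the first dose. Neither assessment is scheduled again before Day 28 (vital signs) or Day 50 (physical examination). Only hyperphagia has no scheduled predose source of this kind.

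The reach is limited as well. None of the solicited terms in SAP Table 3 is on the list. The listings of serious events and discontinuations are not described as restricted by phase. Measured blood pressure is graded for treatment emergence separately (SAP 5.6.3.2).

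Most of this stands, and it limits the size of the point. It does not remove it. The header as written sets no time or source condition, and the narrow reading still works through a list that contains non-laboratory terms. That some blood pressure and lymph node findings precede dosing is a reason to use the recorded time, not the date alone.

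A reader might infer that post-dose clinical events are in fact being removed, or that the date rule is wrong for the whole list. The documents support neither. No affected event is shown, and for true laboratory terms the predose sampling makes the rule reasonable.

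**Conclusion.** Wrong as written (minor). Appendix 8 conflicts with SAP 5.6.2, SAP Table 1 and protocol 9.4.4.1, and 3 of its 83 terms are not laboratory results. A Day 1 event with one of those terms that starts after the first dose can be moved out of the treatment-emergent tables.

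The effect is limited to onsets on the date of first intake and is probably small. It goes in one direction only. The rule takes no account of treatment group, so it is not in itself a bias for or against either dose regimen; what it can understate is the absolute emergent incidence.

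This rests on two assumptions: that the programming follows the Appendix 8 header or its list as worded, and that Day 1 safety samples were drawn predose as scheduled. If no Day 1 event carries one of the three terms, the tables are unaffected by this point.

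**What to change.** 1. Remove lymphadenopathy, blood pressure increased and hyperphagia from Appendix 8.
2. Classify Day 1 events with these terms by recorded onset time against the time of first intake. Findings from the predose screening visit stay in screening. If the time is missing and no predose source is documented, use the existing 5.6.2 default of treatment-emergent.
3. Keep the screening assignment for laboratory terms that rest on the predose Day 1 sample. Judge this by the sample time, not by when the result was reported; a time condition on the adverse event record itself could turn a baseline abnormality into an emergent event. Protocol section 8 already requires sample dates and times in the case report form.
4. Reword the Appendix 8 header and 5.6.2 so that they state the same rule, and list it in SAP Appendix 2 as a departure from protocol 9.4.4.1.

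The cost is a list edit, two sentences of SAP text and a small change to the phase derivation. The documents describe no field linking an adverse event to a sample, so the few Day 1 records whose source is unclear may need manual review.
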